One such use of ureteral stents is temporary stenting following ureteroscopic treatment of upper urinary tract stones. These stones can range in size from a few millimeters to a few centimeters and are generally made up of mineral and acid salts, with 70-80% of kidney stones being made of calcium oxalate. The remaining make up of stones are split by those composed of struvite, uric acid and calcium phosphate. (Satyanand, Patel, Patel, Tarun, & Soniya, 2012) In a 2007-2010 survey showed kidney stone prevalence in the United States population estimated to be 10.6% for men and 7.1% for women with an overall unadjusted prevalence to be 8.8%. (Ziemba & Matlaga, 2017)

Treatment decisions for stones are determined at the individual case level and take into account stone size, stone location, and (if known) stone composition, as well as patient preference and physician expertise. Current treatment recommendations are generally endourologic procedures such as ureteroscopy (URS), shock wave lithotripsy (SWL), and percutaneous nephrolithotomy (PCNL). (Türk, et al., 2016) Ureteral stents are placed after ureteroscopy for stone removal to prevent pain (Torricelli, De, Hinck, Noble, & Monga, 2014) and to aid in future removal of residual stone fragments. (Chen, Tsai, Yu, Wu, & Lin, 2013) Thus, ureteral stents are a fundamental part of a urologic stone practice. Further, ureteral stents have been used for maintaining luminal patency in ureteral obstruction, including cases of malignant ureteral obstruction due to pelvic malignancy. If urine flow to the bladder is not possible, a ureteral stent is placed in the kidney to facilitate drainage following ureteral conduit construction and urinary diversion procedures; rerouting of urine flow to an opening in the wall of the abdomen (stoma). This stenting provides greater assurance of sustained internal urinary diversion, in addition to lessening concerns regarding anastomotic leaks from the pouch.

While usually used temporarily, occasionally patients may have long-term stent placement. Long-term indwell of a ureteral stent increases the risk of encrustation (accumulation of urine salts on the surface of the stent) and can lead to serious and difficult complications such as ureteral obstruction and renal impairment. The most common contributors to encrustation include urinary tract infection, extended indwell times (for chronic strictures or forgotten stents), urinary composition (hypercalciuria, hyperoxaluria, hypocitraturia, homocystinuria, and hyperuricosuria), and history of urolithiasis. Severely encrusted and retained stents are

serious and complex cases for the Endourologist to treat. Since encrustation most often occurs in the bladder and kidney, they often require a multimodal endoscopic approach to achieve stent-free status. (Mohan-Pillai, Keeley, Maussa, Smith, & Tolley, 1999)

Beyond encrustation, another area of interest in ureteral stents is patient discomfort. Ureteral stent pain is a known side-effect of indwelling stents. There have been various studies to determine the best way to measure and decrease the pain associated with ureteral stents with no apparent resolution for the issue. It is hypothesized that a stent composed of a soft flexible material may reduce stent related discomfort. A randomized controlled study of 155 subjects showed a significantly higher incidence of dysuria, renal, and suprapubic pain in those subjects who received a firm polyurethane stent versus a soft stent. (Koprowski, Kim, Modi, & Elsamra, 2016)

Other published studies have explored the duration of time the stent is left in place, (Ozgur, Ekici, Yuceturk, & Bayrak, 2013) use of image guidance in stent placement, (Grasso, et al., 2013) length and other physical features of the inserted stent, (Calvert, et al., 2013) and efficacy of pre-stenting prior to ureteroscopy. (Torricelli, De, Hinck, Noble, & Monga, 2014)

4.2. *Study Rationale*

Under normal conditions, urine is carried from the kidneys to the bladder via the ureters. A ureter may become obstructed as a result of a number of conditions including kidney stones, tumors, blood clots, postsurgical swelling, or infection. When the urine flow is blocked, it backs up into the kidney, which can lead to kidney swelling or hydronephrosis, as well as severe pain in the abdomen, flank, or side; nausea; vomiting; and hematuria. The goal of treatment for ureteral obstruction is to relieve or reduce the blockage and restore urinary drainage. Ureteral obstruction is commonly treated via placement of a ureteral stent; a thin, flexible tube that is threaded into the ureter and restores the flow of urine to the bladder. The most common reason for urinary diversion is bladder cancer that requires the bladder to be removed, a procedure called a cystectomy. Urinary diversion creates a new way for urine to exit body when urine flow is blocked or when there is a need to bypass the urinary tract.

The patient is usually placed under anesthesia for stent insertion, ensuring that the patient remains relaxed and immobile during the procedure. A cystoscope is inserted into the urethra to the bladder, and the opening to the ureter is identified. In some instances, a guidewire is inserted into the ureter under the aid of a fluoroscope. The stent is loaded onto the guidewire and subsequently advanced over the guidewire by a stent positioner (pusher). Once the stent is in place, the guidewire, positioner, and cystoscope are removed. If retrograde stenting is not possible, patients may have the stent placed percutaneously into the kidney, and subsequently into the ureter. Postoperative urine flow is monitored to ensure the stent has not been dislodged or obstructed. The stent may remain in place on a short-term (days to weeks) or long-term (weeks to months) basis and is removed most often cystoscopically. A

stent may also be removed with the attached retrieval line by a physician or nurse in an office setting or by the patient at home.

Although ureteral stents have been used safely in patients for over 30 years, there are limited clinical studies focusing specifically on the safety and efficacy of Boston Scientific's Ureteral Stents. Further, Boston Scientific (BSC) is launching the Tria™ Ureteral Stent (available in Soft and Firm durometers) with proprietary Percushield™ surface technology aimed at reducing calcium and magnesium urine salt accumulations. The goal of this registry is to collect real-world clinical data on BSCs Ureteral Stents to address changing European Regulatory requirements. In contrast to the limited published data for safety and efficacy of BSC Double-J Ureteral Stents, there are published clinical data sets on stent-related pain and Quality of Life (QoL), with many of studies showing increased side effects and reduced QoL associated with stent indwell (Scarneciu, Lupu, Pricop, & Scarneciu, 2015) (Lingeman, Preminger, Goldfischer, & Krambeck, 2009). This study will use a simplified patient QoL questionnaire to measure BSC stent-related pain at various times during the study; medications prescribed post-procedure will also be captured. These QoL data sets will be the first generated for the Tria™ stent family.

5. Commercial Device Description (part of Standard of Care)

5.1. *Commercial Device*

BSC offers a broad portfolio of Ureteral stents. A few Market-approved and commercially available stents are included in this registry.

The following market-approved devices will be evaluated:

- Contour™ Ureteral Stent
- Contour™ SureDrive™ Steerable Ureteral Stent
- Contour VL™ Ureteral Stent
- Contour VL™ SureDrive™ Steerable Ureteral Stent
- Contour™ Injection Ureteral Stent
- Contour VL™ Injection Ureteral Stent
- Percuflex™ Ureteral Stent
- Percuflex™ Plus Ureteral Stent
- Percuflex™ Plus SureDrive™ Steerable Ureteral Stent
- Polaris™ Ultra Ureteral Stent
- Polaris™ Loop Ureteral Stent
- Tria™ Soft Ureteral Stent
- Tria™ Firm Ureteral Stent
- Percuflex™ Urinary Diversion Stent

The above list of devices could be expanded to include other BSC Ureteral Stent devices in this registry.

A copy of the device labeling and Instructions/Directions for Use (IFU/DFU) will be provided in local language(s) as required per national regulation. An Investigational Brochure has not been developed and per ISO 14155 is not required for this postmarket observational clinical investigation as commercial product information is available and study device(s) are used within the approved indication.

Appendix 1 provides a detailed list of all BSC Ureteral stents available to be used in the study along with their respective UPN/Product code.

5.2. *Medical Equipment Description*

Accessories that will be used in conjunction with the placement of a BSC Double-J Ureteral Stent during the procedure include the pigtail straightener and stent positioner. BSC ureteral access sheaths and BSC guidewires may also be used. Accessories that may be used in conjunction with the placement of a BSC UDS during a urinary diversion procedure include guidewire, catheter adaptors and drainage bag connector.

5.3. *Device Accountability*

Boston Scientific will not conduct investigational device accountability as required per ISO 14155 as all study devices are commercially available products and are being used within their approved indication. The study devices shall be maintained per each institutions standard practice.

6. Study Objectives and Endpoints

The objective of this study is to compile characteristics of real-world safety and efficacy outcomes for Boston Scientific Corporation's commercially approved Ureteral stents, when used according to the applicable IFU/DFU.

OBJECTIVES	ENDPOINTS	JUSTIFICATION FOR ENDPOINTS
Primary		
The primary objective is to assess the clinical safety and efficacy of BSC Ureteral Stents	Primary safety endpoint: Serious Adverse Device Effects (SADE)	A ureteral stent is placed to open the ureter to allow passage of urine from the kidney, or from the kidney to the bladder. Any

OBJECTIVES	ENDPOINTS	JUSTIFICATION FOR ENDPOINTS
	
Primary efficacy endpoint: For all stents except UDS: Technical Success of the stents defined as Stented kidney drains (to bladder) during the planned indwell time with no re-intervention due to obstruction of the stented ureters
 
For UDS: Technical success defined as drainage following stent placement during the planned indwell time with no re-intervention due to obstruction
	unplanned re-intervention due to an obstructed ureter would mean that there is not drainage from the kidney and the study stent failed to work as indicated, and there is an adverse event or serious adverse device event related to the stent such as urinary retention, dislodging or migration of the stent
Additional		
Quality of Life (QoL) (questionnaires)	
Patient-Reported Outcomes Measurement System (PROMIS®) –
 
 • PROMIS Adult Short Form v1.0 – Pain Intensity 3a • PROMIS Adult Short Form v1.0 – Pain Interference 6b 	Gain information specific to the patient's pain scale and quality of life for subjects treated with ureteral stents
Ureteral Stent Migration	
Defined as any post procedure movement of the stent (i.e., either proximally towards the kidney or distally towards the bladder or complete distal migration) from its implant location; confirmed via imaging where necessary
 
Note: Movement of a stent by external force or inadvertent pulling is not considered a stent migrations.
	Capture real-world stent migration rates

7. Study Design

The Double-J PLUS Registry is a prospective, on-label, multi-center, global registry.

7.1. *Scale and Duration*

The registry will include:

- Up to 1,000 subjects will be enrolled at up to 35 sites
- At least 142 subjects will be enrolled for Tria™ Ureteral stent for stone management at sites within the United States, Europe, Canada and Japan. A hypothesis test will be performed for this patient group.
- Target enrollment for each additional stent type as outlined below.
- The enrollment period will be approximately 30 months.
- There will be up to 15 sites in the United States; 10 in EU, 5 in Canada and 5 in Japan.
- The study is expected to take 50 months from first subject enrollment until the study closeout.
- Each subject will be involved in the study for approximately 8 weeks to 15 months depending on the stent indwell time, from the index procedure.

Boston Scientific Ureteral Stents	Target Enrollment	Minimum Target Enrollment
• Tria Soft and Tria Firm	142	142
• Polaris Ultra	25	15
• Percuflex	25	15
• Contour Injection	30	15 each
• Contour VL Injection		
• Contour	30	15 each
• Contour SureDrive Steerable		
• Contour VL	30	15 each
• Contour VL SureDrive Steerable		
• Percuflex Plus	30	15 each
• Percuflex Plus SureDrive Steerable		
• Polaris Loop	25	15
• Percuflex UDS	25	15

[figure not shown]

Figure 7.1: BSC Ureteral Stent Registry Study Design

7.2. *Treatment Assignment*

This is a post-market registry study and any subject who intends to receive BSC Ureteral Stent(s) or Urinary Diversion Stent(s) and is willing to provide a written informed consent will be approached and considered for enrollment in the study. Subject is considered enrolled in the study once the subject has signed the informed consent form. Each subject will be assigned a unique subject identifier in the Electronic Data Capture (EDC) system.

7.3. *Justification for the Study Design*

BSC Ureteral Stents are commercially available devices to relieve or reduce ureteral blockage and restore urinary drainage. With a cohort study design, enrolling subjects receiving the stent as standard of care procedure will provide real-world data.

8. *Subject Selection*

8.1. *Study Population and Eligibility*

Up to 1,000 implanted subjects may be included in the registry.

Subjects will generally be recruited from physician's practice and subject must meet the indications for a ureteral stent implant per the IFU/DFU. Patients who meet all of the following criteria (see Table 8.2) may be given consideration for inclusion in this clinical investigation, provided no exclusion criterion (see Section 8.3) is met.

8.2. *Inclusion Criteria*

Subjects who meet all of the following criteria (see Table 8.2) may be given consideration for inclusion in this clinical investigation, provided no exclusion criterion (see Section 8.3) is met.

Table 8.1: Inclusion Criteria

Inclusion Criteria	
For all ureteral stent types except UDS:
 
 1. Subject is undergoing placement of a Boston Scientific Ureteral Stent(s) included in the registry 2. Subject anatomy is appropriate to accommodate a stent size available in the study 3. Subject is able to accurately detect and report bladder function and pain 4. Subject is willing and able to: 
 a. Complete patient QoL questionnaire at specified time points (for subjects aged \geq 18 years) b. Return for all follow-up visits 
For UDS:
 
 1. Subject is undergoing placement of a Boston Scientific Urinary Diversion Stent(s) 2. The anatomical features of the involved renal collecting system are known by either prior or concurrent urography or axial imaging 3. Subject is willing and able to Return for all follow-up visits
---------------------------	--

8.3. *Exclusion Criteria*

Subjects undergoing placement of a BSC US or UDS who meet any one of the following criteria (Table 8.3) cannot be included in this study or will be excluded from this clinical study. For subjects receiving bilateral/multiple stenting, the final exclusion criterion is confirmed during the stent placement procedure.

Table 8.2: Exclusion Criteria

Exclusion Criteria	
 1. Subject meets any of the contraindications as per individual stent IFU/DFU 2. Subject receiving different stent type in case of bilateral/multiple stenting 3. Subject with an indwelling ureteral stent(s) not planned to be removed prior to/or concurrently with the study stent implant
---------------------------	--

9. Subject Accountability

9.1. *Point of Enrollment*

Subjects will be considered enrolled in the study after he/she signs and dates the informed consent (ICF). No study specific (non-standard of care) procedure(s) or assessment(s) can take place until the informed consent is signed.

9.2. *Withdrawal*

All subjects enrolled in the clinical study (including those withdrawn from the clinical study) shall be accounted for and documented. If a subject withdraws from the study, the reason(s) shall be reported. If such withdrawal is due to problems related to device safety or performance, the investigator shall ask for the subject's permission to follow his/her status/condition outside of the clinical study.

Reasons for withdrawal include but are not limited to physician discretion and subject choice to withdraw consent. While study withdrawal is discouraged, subjects may withdraw from the study at any time, with or without reason, and without prejudice to further treatment. All applicable electronic Case Report Forms (eCRFs) up to the point of subject withdrawal and an End of Study eCRF must be completed. Additional data may no longer be collected after the point at which a subject has been withdrawn from the study or withdraws his/her consent. Data collected up to the point of subject withdrawal may be used for study analysis, unless local regulations apply.

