9.5. End-of-Study Definition

A clinical study at each participating site is considered completed when participants are no longer being examined or the last participant's last study visit has occurred, and study closeout activities are completed

A subject is considered to have completed the study after he or she has completed all phases of the study including the last visit shown in the Data Collection Schedule (see section 10) or if the study stent is replaced either for planned stent replacement or due to re-intervention.

The end of the study is defined as completion of the final Clinical Study Report.

10. Study Methods

10.1. *Data Collection*

The data collection schedule is shown in Table 10.1. Assessments will be completed based on standard of care practices at the site and PROMIS® pain scale questionnaires will be collected. All study data will be recorded on source documentation and captured within electronic Case Report Forms (eCRFs) for the purposes of this study. Study data will be monitored by Boston Scientific or representatives and as applicable on a regular basis as outlined in the study Monitoring Plan.

Table 10.1: Data Collection Schedule

Procedure/Assessment	Screening/ Enrollment Baseline Visit	Index Procedure (≤ 45 days from Baseline visit)	Post-Procedure Visit	Follow-up Visits		
			Only if Long term indwell of greater than 90 days (45 – 90 ² days from Index procedure)	Stent Removal Visit (< 365 ² days from Index procedure)	Post-Stent Removal visit (3-12 weeks from Stent Removal)	Unscheduled Visit
Informed consent process, including informed consent signature date ¹	X					
Inclusion/Exclusion Criteria	X	X ²				
Demographics	X					
Medical History	X					
Laboratory – Blood Test, Serum Creatinine and Glomerular Filtration Rate (GFR)	X				X ⁵	X
Laboratory – Urinalysis/Culture UTI status and Pregnancy test ⁴	X					X
Physical Assessment: Weight, Height, BMI, and Temperature	X					
QoL Questionnaires (PROMIS®) (Except for UDS):- Adult Short Form v1.0 – Pain Intensity 3a -Adult Short Form v1.0 – Pain Interference 6b	X - Prior to Implant			X - Prior to Removal	X	
Assessment of Adverse Events (including Clavien- Dindo Classification) and Device Deficiencies (including stent migrations and stent dislodgements)		X	X	X	X	X
Stent Performance Assessment		X	X	X		X
Boston Scientific Accessory Device Assessment		X				

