10.5. Baseline Visit [up to 45 days prior to Index procedure]

The Baseline Visit will occur prior to the subject having index procedure/stent placement. The assessments below must be completed prior to index procedure and may occur up to 45 calendar days prior to index procedure.

The baseline assessments below can be completed on the same day as Index procedure, prior to the stent implant.

- Demographics: Age, Gender, Race and Ethnicity
- Diagnosis/Medical History (only active medical problems at the time of baseline assessment, including Neoadjuvant chemotherapy (within 6 months prior to stent placement for bladder cancer); Radiation status (pelvis and abdomen))
- Labs: Serum Creatinine, GFR
- Urinalysis/culture: UTI status, Pregnancy test for women of child-bearing potential
- Physical examination: Height, Weight, BMI, Temperature
- COVID-19 assessment: prior diagnosis, test result, vaccination status (if available)
- QoL Questionnaires (PROMIS):
 - Adult Short Form v1.0 – Pain Intensity 3a
 - Adult Short Form v1.0 – Pain Interference 6b

Note: QoL Questionnaires not required for subjects receiving UDS

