11.3.1. Other Endpoints/Measurements

11.3.1.1. Additional Endpoint 1 - QoL

To evaluate the change in quality of life as measured by Patient-Reported Outcomes Measurement System (PROMIS®) at Stent Removal Visit compared to Index Procedure.

The endpoints are Pain Interference assessed by the PROMIS Short Form v1.0 - Pain Interference 6b instrument, and Pain Intensity assessed by the PROMIS Scale v1.0 – Pain Intensity 3a scale.

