11.3.1.1.1 Statistical Methods

Descriptive statistics including 95% confidence intervals will be used to summarize the pain interference and pain intensity at Index Procedure, and Stent Removal Visit along with change from Index Procedure for each ureteral study stent type implanted respectively (excluding urinary diversion stents).

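### Some baseline PROMIS scores will be taken with an earlier stent in place, so the pooled change per stent type is pulled toward zero by a share of subjects that the plan does not record

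*Combined protocol and SAP*

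**What the plan says.** **Eligibility.** Criterion 3 in the exclusion table of section 8.3, repeated in the synopsis, excludes a "Subject with an indwelling ureteral stent(s) not planned to be removed prior to/or concurrently with the study stent implant". A subject whose existing stent is due to come out before or during the study implant does not meet it and may enter.

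**Timing of the first score.** Table 10.1 marks PROMIS in the screening/baseline column as "X - Prior to Implant". Section 10.5 lists the two questionnaires among the baseline items and says: "The assessments below must be completed prior to index procedure and may occur up to 45 calendar days prior to index procedure". Section 10.6, which lists the data collected at the index procedure, has no PROMIS.

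**Contrast.** Section 11.3.1.1 defines the endpoint as the change in PROMIS "at Stent Removal Visit compared to Index Procedure". Section 11.3.1.1.1 will "summarize the pain interference and pain intensity at Index Procedure, and Stent Removal Visit along with change from Index Procedure", by stent type and without urinary diversion stents. The removal-visit score is taken before the stent comes out (section 10.8).

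**Purpose.** Section 4.2 states: "This study will use a simplified patient QoL questionnaire to measure BSC stent-related pain at various times during the study".

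**Separation of subjects.** Neither section 10.5 nor 10.6 names an existing stent as a data item. Subgroups are by indication (section 11.3.3), and section 11.3.5 plans no multivariable analysis.

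**The concern.** A change from baseline measures the effect of having a stent only if the baseline is stent-free. The protocol itself says: "Ureteral stent pain is a known side-effect of indwelling stents". A subject who answers the baseline questionnaire with an old stent in place therefore brings stent symptoms into the reference score, and that subject's change compares one stent with another.

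The protocol acknowledges the practices that produce such subjects: pre-stenting before ureteroscopy and long-term drainage (section 4.1), and planned stent replacement (section 9.4). The indication subgroups do not separate them, because a first-time and a pre-stented stone patient both count as stone management.

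What is at stake is how the change score can be read. Section 4.2 says that these will be the first quality-of-life data for the Tria family. A mean that mixes stented and unstented baselines in an unknown proportion cannot be read as the pain that a stent adds. If stent status at baseline is not recorded, the mix may not be recoverable at analysis.

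**Working it through.** The plan states no effect size, standard deviation or power for PROMIS, so there is no figure to reproduce. The check has two parts.

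**1. Which score is the baseline?**
- The analysis refers to a score at the index procedure, but sections 10.5 and 10.6 and Table 10.1 provide only a pre-implant score, taken 0 to 45 days before the procedure.
- Old stent removed at the implant: the baseline score is taken with a stent in place.
- Old stent removed after the baseline visit but before the implant: likewise.
- Old stent removed before the baseline visit: the score is stent-free, but it may follow removal closely.

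**2. What does pooling do to the mean change?** The inputs below are assumptions, because the documents supply none of them:
- f: share of a stent type's subjects with a stent in place at the baseline PROMIS
- D: mean change in subjects without a stent at baseline
- C: mean change in subjects with a stent at baseline

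Pooled mean change = (1-f)D + fC. The shift from D is therefore f(C-D).

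If old and new stents hurt about equally, C is near 0 and the pooled mean is about (1-f)D:

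| f | D = +5 | D = +2 | D = 0 | D = -5 |
|---|---|---|---|---|
| 0% | 5.0 | 2.0 | 0 | -5.0 |
| 10% | 4.5 | 1.8 | 0 | -4.5 |
| 25% | 3.75 | 1.5 | 0 | -3.75 |
| 50% | 2.5 | 1.0 | 0 | -2.5 |
| 100% | 0 | 0 | 0 | 0 |

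The pull is toward zero for either sign of D, and its relative size is f.

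For scale, most non-Tria types have a minimum target of 15 subjects (section 7.1). At n = 15, one subject with a stented baseline and no change moves that type's mean by 1/15, about 7% of D.

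**The case against.** **Direction.** A reader might infer that the pooled change must understate stent pain. The documents do not support that. Section 4.1 says stents cause pain, but section 4.2 says a blocked, unstented ureter can itself be very painful. If relief of obstruction outweighs stent discomfort, D is negative, and stented baselines make an improvement look smaller. This objection stands, so the direction has to be stated conditionally.

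**Size.** f, D and a near-zero C are all assumed. C could differ from zero if the old and new stents differ, or because the index procedure itself affects pain. This stands, and the table is illustrative only.

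**Spurious differences between stent types.** A reader might infer that types will appear to differ through case mix alone. With D = 5, shares of 10% and 50% would give 4.5 and 2.5, a gap of 2.0 points. But the plan makes no between-type comparison, and nothing in the documents shows that the share differs by type. This is a caution for anyone who sets the columns side by side, not a defect in a planned test.

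**Other information.** The score at stent removal is reported with a confidence interval and does not depend on the baseline. PROMIS is also collected after removal (section 10.9). Both help, but the post-removal score is not in the planned contrast, and the change score remains mixed.

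**Data capture.** The eCRFs are not among the documents, and sites must establish any existing stent in order to apply criterion 3. Section 10.5 also collects active medical problems. So it cannot be shown that the item goes uncollected, only that the plan neither names it nor uses it.

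**Restricting the analysis.** Making stent-free baselines the main summary would leave very few subjects in some types, and obstruction pain would still be in the baseline. This stands. Showing both groups is enough.

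**Conclusion.** The mechanism follows from the plan's own text: already-stented subjects are eligible, their only baseline PROMIS may be a stented one, and the change is pooled by stent type with nothing named to identify them. For those subjects the change compares new stent with old.

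If they change little, the pooled mean is about (1-f)D, a pull toward zero by the fraction f. It understates added stent pain if D > 0, makes an improvement look smaller if D < 0, and has no effect if D = 0. The size is unknown, because the documents give neither f nor D.

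The consequence is limited. PROMIS is an additional, descriptive endpoint with no hypothesis. The Tria technical-success test and its sample size do not depend on it. The case for change is that a cheap addition would let the change score serve the aim in section 4.2.

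**What to change.** 1. Add to the baseline data in section 10.5 and to the eCRF: *ureteral stent in place at the time of the baseline PROMIS (yes/no, side); if removed before baseline, date removed*.
2. In section 11.3.1.1.1, keep the overall summary for each stent type and also report the change separately for subjects with and without a stent in place at the baseline PROMIS.
3. Optionally, add the contrast between the Stent Removal and Post-Stent Removal PROMIS scores, which are already collected (sections 10.8 and 10.9), as a stent-free reference. State that it will be missing where the study stent is replaced, because participation then ends (section 9.4).

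Eligibility, visits and care do not change. The cost is one eCRF item, largely information that sites need anyway for criterion 3, and extra table columns. Strata will be small for stent types with about 15 subjects, so their intervals will be wide.
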